The University of Pittsburgh will be the coordinating center for the multi-center project "Remote Wheelchair Skills Training Efficacy." The University of Pittsburgh will coordinate most aspects of this multi-center project. We will be responsible for the design and development of the protocol and consent templates and data collection forms. We will also assist with the tracking of enrollment. We will be responsible for tracking, reporting, and maintaining serious adverse events and unanticipated problems involving risk to subjects or others, and dissemination of information to all sites. In addition, we will provide periodic updates to sites on the study on enrollment, progress, and any other relevant information. We may also monitor each site to assess study progress, protocol adherence, consenting processes, and accuracy of research records. The University of Pittsburgh will also be responsible for overseeing the analysis of data collected from this study.

We will also review and moderate the web environment where the training materials are hosted. Through this, we will have access to video and/or photographs of training tasks being completed by participants. The coordinating center will provide feedback to participants on the training tasks.

Note that copies of training records, licenses, certificates should be maintained in the study regulatory binder and are subject to audit by the Research Conduct and Compliance Office (RCCO).

CC1.1 Projected number of subjects to be enrolled at all study sites:
96

Reviewer notes- J

This application is specific to the coordinating center research activities. It does not include the local site research activities. Each site must obtain approval from their respective local IRB.

The investigator must upload the applicable protocol and consent templates, drug, device, or biologic information for review purposes only. The IRB will determine if the center has mechanisms in place to ensure that the management, data analysis, and data/safety monitoring systems are adequate.

- **DO NOT** list any of the sites in questions CC3.0 or CC4.0 until site authorization or local IRB approval has been obtained. List potential sites in the Abstract, question CS2.1.
- Once local site approval is obtained, submit a **Modification** to upload the approval notification.
- A **Modification** must be submitted if revisions to the protocol and/or consent form result in changes to the responsibilities of the coordinating center as described below.
 - Changes to Exempt projects require use of 'Send comments to IRB staff' so the IRB can determine if the project still meets the exemption criteria or if a new application needs to be submitted.

Section: Coordinating Center

Important: If subjects will be enrolled at this site, a separate local site application must be submitted.

Has the Coordinating Center PI assumed the responsibility for the following?

cc2.1 Design and development of the protocol and/or consent template: Yes

CC2.2 * Design and development of case report forms/ data collection tools: Yes

CC2.3 Randomization, registration, and/or tracking subject enrollment: Yes

If Yes, describe the process:
The Coordinating Center will be responsible for developing the study protocol and/or consent templates. The templates will then be provided to the participating centers, so that they can submit the project to their local IRB. Sites will be instructed to modify the templates to include their site specific information and to meet the requirements of their local IRB. The executive committee, which will consist of the project directors at each participating center will be responsible for tracking subject enrollment. The executive committee will have regularly scheduled conference calls to discuss study progress including enrollment. Enrollment will be tracked using a tracking sheet.

CC2.4 * Tracking, reporting, and maintaining serious adverse events and unanticipated problems involving risk to subjects or others, and dissemination of information to all sites: Yes
* 1) If Yes, the mechanism to be employed and 2) if No, indicate who (by role) is responsible:
All serious adverse events and unanticipated problems involving risks will be recorded on paper forms. Participating sites will be asked to fill out the adverse event form and send it via email to the Coordinating Center PI within 10 working days of learning of the event. This e-mail will be forwarded to the University of Pittsburgh IRB and other participating sites to notify them of the event within 10 working days of receipt by the coordinating center.

CC2.5 * Providing periodic updates to all sites on subject enrollment, study progress, amendments and relevant scientific advances: Yes
1) If Yes, the mechanism to be employed and 2) if No, indicate who (by role) is responsible:
The coordinating center will have regularly scheduled conference calls with the executive committee to discuss overall project direction, problems that arise, and new research findings. During each conference call, the progress at each site will be reviewed and discussed and potential barriers to project progress and their solutions will be identified. The executive committee will also be responsible for any changes to the protocol and documentation for human subjects protection. All site Principal Investigators will be held accountable for the progress of their portion of the project. Minutes will be taken during each conference call to formally document progress and identify specific action items. A list serve will also be created to provide a method of communication with all participating sites.
Sites will be sent periodic emails regarding participant progress through the training materials. Emails may occur weekly while the participant is active in the study.

CC2.6 Monitoring/auditing each site to assess study progress, protocol adherence, consenting processes, accuracy of research records: Yes
1) If Yes, the mechanism to be employed and 2) if No, indicate who (by role) is responsible:
The coordinating center will have regularly scheduled conference calls with the executive committee to assess the study progress and ensure that the participating centers are adhering to study procedures outlined in the study manual of operation. It is the responsibility of the site Principal Investigators to ensure that their staff are obtaining informed consent prior to conducting any study procedures. The original research files will

function: Coordinating Center

be stored at each of the participating sites. Each site will be responsible for ensuring that their research data/documents are restricted to associated investigators and research staff. Each site will be asked to keep research files under double lock and key and be only accessible to authorized study personnel. The coordinating center may conduct site visits to monitor protocol implementation, data collection procedures at each site, documentation, and to provide consultation on study implementation issues. The coordinating center may also complete periodic cross-checks of the data to ensure its quality.

CC2.7 Ensuring that the affiliated sites are using the correct version of the IRB protocol and consent documents and maintaining IRB approval throughout the conduct of the study: Yes

1) If Yes, the mechanism to be employed and 2) if No, indicate who (by role) is responsible:

The Principal Investigator at each site will be responsible for ensuring that the correct versions of the IRB protocol and consent document are being used throughout the study. The site Principal Investigator will also be responsible for maintaining IRB approval by ensuring renewals are submitted in a timely manner. Each site will be required to send the coordinating center a copy of their initially approved protocol and consent document as well as continuing review and modification approvals.

CC2.8 * Data management, including transmission, storage, and analysis: Yes

If Yes, indicate if only de-identified data will be received, describe the process and tools to be used to ensure confidential transmission/storage, and analysis of the data:

The original research files (including the consent forms) will be stored at each of the participating sites. Each site will be responsible for ensuring that their research data/documents are restricted to associated investigators and research staff. Each site will be asked to keep research files under double lock and key and be only accessible to authorized study personnel.

Data will be collected using paper and pencil or using the web-based system Qualtrics. Security measures including log-in procedures for data entry that will be restricted to associated research staff will be implemented. Participant confidentiality will be preserved by linking participant names to numeric IDs at the study sites. This linkage code file will be stored securely at the study sites.

The coordinating center will receive coded data from the participating centers through Qualtrics. We may also receive images and videos of the training tasks from participants through Qualtrics.

CC2.9 * Distributing or storing drugs and/or devices: N/A

1) If Yes, the process for distribution and 2) if No, indicate who (by role) is responsible:

CC2.10 * Indicate other responsibilities not listed above:

The coordinating center will also be responsible for developing the manual of operations for this study.

CC2.11

Describe the steps that will be taken to ensure that each external site is fully informed of study procedures and requirements prior to its initiation of research procedures. Also describe what steps will be taken to ensure regulatory compliance.

To ensure that all sites are fully informed of study procedures and requirements prior to clinical testing we will conduct in person training sessions and/or teleconferences to educate all sites on the manual of operations developed, ensuring participant confidentiality and data security. The training session(s) will educate all investigators to ensure data integrity and standardized data collection. Topics for discussion during the training include recruitment methods, informed consent, eligibility criteria, and data collection. We will also develop and distribute a sample IRB protocol, consent form, recruitment flyer, and data collection forms to all sites.

ection: Coordinating Center

CC2.12 Is the center responsible for the long-term storage (banking) of biological specimens?

No

If Yes, broadly describe the intended future use, storage and distribution process:

[reviewer notes.]

CC3.0

Will this research be conducted in (a) a foreign country and/or (b) at a site (e.g., Navajo Nation) where the cultural background of the subject population differs substantially from that of Pittsburgh and its surrounding communities?

No

[reviewer notes.]

CC4.0

Address the following for each U.S. site where this research will be conducted:

- Name of site or institution
- Approval letter from a local IRS for this site and date of initial approval
- Append a copy of either a letter of authorization to conduct the research at the facility or a signed statement of work
- Name and qualifications of the local collaborator
- If Federally funded, provide the Federalwide Assurance number (FWA) assigned to the site

Site	Date Modified
View Midwest Regional Spinal Cord Injury Care System	6/12/2018
View Northern New Jersey Spinal Cord Injury System	3/11/2018
View South Florida Spinal Cord Injury System	6/25/2018
View University of Pittsburgh Model Center on Spinal Cord Injury	5/13/2018

Midwest Regional Spinal Cord Injury Care System (FWA: FWA: 00001549)

Has local IRB or ethical review been obtained for this site? yes

Has authorization to conduct research at this facility been obtained? yes

Approval Letter(s): Approval

Date of Local Approval: 6/22/2018

function: Coordinating Center


CSIS.O

Indicate the sites where research activities will be performed and/or private information will be obtained.

Choose all sites that apply and/or use Other to include sites not listed:

Sites:

University of Pittsburgh

University of Pittsburgh

Campus:

Main Campus - Pittsburgh

List university owned off-campus research sites if applicable:

ection: Cover Shee

If you selected School, International or Other, list the sites:

*For research being conducted at non Pitt or UPMC sites, upload a site permission letter granting the researcher permission to conduct their research at each external site:

Name Modified Date

CS15.1 Have you, [name], verified that all members of the research team have the appropriate expertise, credentials, and if applicable, hospital privileges to perform those research procedures that are their responsibility as outlined in the IRB protocol?

* Yes

CS15.2 Describe the availability of resources and the adequacy of the facilities to conduct this study:

Adequate staff, time and funds have been allocated to coordinate this multi-site project. The PI, co-investigators and staff working on this project have previous experience coordinating multi-site projects.

!Section: Section 1 - Objective, Aims, Background and Significance!

[reviewer notes-]

1.1 Objective: What is the overall purpose of this research study? (Limit response to 1-2 sentences.)

The objective of the study is to evaluate the effectiveness of remote training to teach clinicians how to train others in wheelchair skills.

1.2 Specific Aims: List the goals of the proposed study (e.g., describe the relevant hypotheses or the specific problems or issues that will be addressed by the study).

Evaluate the ability of remotely trained clinicians (trainers) to teach other individuals (trainees) using the skills and techniques presented in the Wheelchair Skills Training Program (WSTP) by evaluating:

- 1) Wheelchair skills capacity of trainees.
- 2) Wheelchair skills confidence of trainees.

Section: Section 2 - Research Design and Methodology[reviewer notes.]**2.17 What are the main outcome variables that will be evaluated in this study?**

The main outcome variables are to determine the effectiveness of remote wheelchair skills training include the Wheelchair Skills Test Questionnaire questions on capacity (WST-Q capacity) and confidence (WST-Q confidence), knowledge questions about wheelchair skills (WST knowledge), and remote evaluation through video analysis by the study team on capacity to perform skills. Additionally, we will gather feedback on how the training process could be improved.

2.18 Describe the statistical approaches that will be used to analyze the study data.

* Addressed below:

We will use a paired t-test to evaluate if there is an improvement in knowledge of skills following the respective training programs through knowledge based questionnaires for the trainees. We will determine if capacity and confidence increases through paired comparisons between baseline and follow-up for the WST-Q total scores. Capacity will also be evaluated based on whether participants are successful in each task as determined by a remote rater; in this success will be determined with at least 75% of participants achieving capacity in each task.

A power analysis was completed based on the published study completed with Occupational Therapy students with a pre-WSTP score of $64.8+/-9.0$ and post-WSTP score of $81.0+/-5.2$. Taking this into consideration, we will need a sample size of 23 individuals for a 95% power to detect a difference in the pre-WSTP and post-WSTP scores. We have estimated a sample size of 24 trainers and 72 trainees to account for participants who do not complete the study.

!Section: Section 5 - Potential Risks and Benefit

[reviewer notes.]

5.2

What steps will be taken in the event that a clinically significant, unexpected disease or condition is identified during the conduct of the study?

Not Applicable

[reviewer notes.]

5.8

Will any individuals other than the investigators/research staff involved in the conduct of this research study and authorized representatives of the University Research Conduct and Compliance Office (RCCO) be permitted access to research data/documents (including medical record information) associated with the conduct of this research study?

Yes

5.8.1

Identify the 'external' persons or entity who may have access to research data/documents and the purpose of this access:

Collaborators of this multi-site study may have access to coded research data collected by other participating sites for data analysis purposes. Images or videos of participants completing wheelchair tasks may be shared for the purposes of data analysis with collaborators as well.

5.8.2

Will these 'external' persons or entity have access to identifiable research data/ documents?

Yes - Describe below:

If Yes, describe how they will protect the confidentiality of the research data:
Images or videos of participants completing wheelchair tasks may be shared for the purposes of data analysis with collaborators as well to assist with the development of the training program and for the training of clinicians. These images will be taken by participants, and every effort will be made to avoid recording identifiable features. Participants will have the option to not participate in the video recording, or to re-record tasks to eliminate identifiable features. As the videos will focus on wheelchair skills or maintenance tasks, the presence of identifiable images should be limited to parts of the wheelchair and/or body positioning.

5.9

Has or will a Federal Certificate of Confidentiality be obtained for this research study?

No

5.10

Question has been moved to 5.17

5.11

Question has been moved to 5.16

!Section: Section 5 - Potential Risks and Benefit

[reviewer notes-]

5.12 Does participation in this research study offer the potential for direct benefit to the research subjects?

Not Applicable - This is a Coordinating Center Application

Describe the benefit:

5.13 Describe the data and safety monitoring plan associated with this study. If the research study involves multiple sites, the plan must address both a local and central review process.

A data safety and monitoring plan will be implemented by having regularly scheduled (at least every 6 months) telephone conference calls for this multi-site study to ensure that there is no change in the benefit/risk ratio during the study and that confidentiality of research data is maintained. In addition, the principal investigator of the coordinating center and the executive committee for the project will discuss the study (e.g. study goals, progress, modifications, documentation, recruitment, retention, data analysis, and confidentiality) and address any issues or concerns. These meetings will be overseen by the principal investigator or designee. Minutes will be kept on file for these meetings. Any instances of adverse effects will be reported immediately using the standard forms and/or procedures set forth by the Institutional Review Board. In addition, investigators and/or coordinators may periodically review study documentation and/or consent forms to ensure that subject's confidentiality is maintained.

[reviewer notes-]

Section 5 - Potential Risks and Benefits of Study Participation

5.15 What precautions will be used to maintain the confidentiality of the research data during collection, transmission and storage? It is important that you indicate the data security measures for all data types.

Go to the [A-Z Guidance](#), download the Data Security Assessment Form, complete, and upload using the Add button below. Depending on the data type, you may need to consult with your data manager to address some of the sections. Email [contact] if you have any questions.

Upload Data Security Form:

Name Modified Date

DSF 2/9/2018 11:29 AM

Address what precautions will be used to maintain the confidentiality of the research data collected in paper format if applicable:

Paper-based records will be kept in a secure location and only accessible to personnel involved in the study. Computer based files will only be made available to personnel involved with this multi-site project through the use of access privileges and passwords. Participant's identity on forms will be indicated by a case number rather than by their name, and the code linking their name to the number will be maintained separately with limited access to associated research staff. To maintain the confidentiality of all data that is transferred to the coordinating center from participating centers, only coded data will be transferred. Questionnaires, images and video may be shared with the coordinating center and collaborators for the purposes of data analysis, further developing the training programs and for the training of clinicians.

Participants may record themselves performing wheelchair skills tasks. Every effort will be

!Section: Section 5 - Potential Risks and Benefit

made to avoid recording identifiable features. Participants will have the option to re-record or not upload any videos that show images they do not wish to share. As the videos will focus on wheelchair skills tasks, the presence of identifiable images should be limited to parts of the wheelchair and/or body positioning. Participants will upload the videos into Qualtrics, with access limited to research staff.

5.15.1

Does your research study require a data security review? Answer Yes if any of the following conditions are met:

- Identifiable or 'coded data will be collected, stored, or transmitted using any of the following technologies: mobile app, web-based site or survey, wearable device, text messaging, electronic audio, photographic, or video recording or conferencing **and/ or**
- The IRB requested a data security review during their review of the study

* Yes

'Coded: Identifying information (such as name) that would enable the investigator to readily ascertain the identity of the individual to whom the private information or specimens pertain has been replaced with a code (number, letter, symbol, or any combination) and a key to decipher the code exists, enabling linkage of the identifying information to the private information or specimens

5.16

If the subject withdraws from the study, describe what, if anything, will happen to the subject's research data or biological specimens.

No subjects will be enrolled under this protocol. If a participant from any of the participating centers withdraws from the study, any information collected prior to the date the subject formally withdrew may continue to be used.

5.17

Following the required data retention period, describe the procedures utilized to protect subject confidentiality. (e.g., destruction of research records; removal of identifiers; destruction of linkage code information; secured long-term retention)

Following the required data retention period, the linkage code information will be destroyed. The coded data collected will be retained for an indefinite period of time and will be stored in a secure manner.

Section: Section 6 - Costs and Payment

Reviewer notes:-)

6.1

Will research subjects or their insurance providers be charged for any of the procedures (e.g., screening procedures, research procedures, follow-up procedures) performed for the purpose of this research study?

*

No

Reviewer notes:-)

6.2

Will subjects be compensated in any way for their participation in this research study?

Yes

6.2.1

Describe the amount of payment or other remuneration offered for complete participation in this research study.

For complete participation, Trainers may receive \$255 or \$345, depending on their participation history.

For complete participation, Trainees will receive \$75.

6.2.2

Describe the amount and term of payment or other remuneration that will be provided for partial completion of this research study.

Participants will be compensated for each portion of the study that they complete.

Trainers will be paid \$30 for completing baseline questionnaires and reviewing online material. They will be paid \$60 for practicing the skills in pairs and sending videos for remote review. Trainers will also receive \$30 for completing the post-training questionnaires and providing feedback on the training program(s). If a participant has completed the above listed activities as part of the study "Remote Training Coordinating Center" (PRO15120300), they will receive \$30 for completing the wheelchair skill modules and the pre-/post-confidence questionnaire.

Trainers will receive \$75 for providing wheelchair skills training to a WSTP Trainee. They may provide training to up to 3 Trainees. For complete participation, they may receive \$255 or \$345, depending on their participation history.

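### The plan sets out to determine the effectiveness of remotely training trainers, but its uncontrolled, unclustered trainee pre-post comparison can show only that their trainees improved

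*Combined protocol and SAP*

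**What the plan says.** The objective in 1.1 is to "evaluate the effectiveness of remote training to teach clinicians how to train others in wheelchair skills". Section 2.17 opens: "The main outcome variables are to determine the effectiveness of remote wheelchair skills training". The remote training is delivered to trainers, whereas the aims in 1.2 are measured in trainees (skills capacity and confidence).

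Section 2.18 plans three paired analyses. For trainee knowledge: "We will use a paired t-test to evaluate if there is an improvement in knowledge of skills". For the two questionnaire outcomes: "We will determine if capacity and confidence increases through paired comparisons between baseline and follow-up for the WST-Q total scores". No minimum gain is attached to any of them. A fourth element concerns remote-rated capacity: "in this success will be determined with at least 75% of participants achieving capacity in each task".

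The power statement in 2.18 uses a published study of Occupational Therapy students, with a pre-training score of 64.8 (SD 9.0) and a post-training score of 81.0 (SD 5.2). It gives 23 individuals for 95% power and plans 24 trainers and 72 trainees to allow for non-completion. Section 6.2.2 lets one trainer teach up to three trainees. It also pays trainers for "completing baseline questionnaires and reviewing online material" and for post-training questionnaires, but 2.18 plans no analysis of trainers' own change.

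**The concern.** The claim and the analysis concern different things. Effectiveness of remote trainer training is a statement about what that training adds. The planned tests ask only whether trainees score higher after being coached than before. Every trainee is taught by a remotely trained trainer, so a gain could reflect the training content, the coaching itself, repeated exposure to the same questionnaire, or skill the trainer already had. Nothing in the design separates these.

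Because the paired tests compare with no change, a gain much smaller than the one used for sizing would be statistically significant. Trainees who share a trainer may also respond alike. A paired analysis that treats them as independent would then give intervals that are too narrow. The risk is a report that remote trainer training is effective, on evidence that cannot show it and with overstated precision.

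**Working it through.** **Inputs from 2.18 and 6.2.2.** SDs 9.0 and 5.2; planning gain 81.0 − 64.8 = 16.2; 23 individuals required; 72 trainees and 24 trainers planned; up to 3 trainees per trainer.

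**Assumptions, not in the documents.** Two-sided alpha 0.05; pre-post correlation r from 0 to 0.7; trainer ICC of change 0.1 to 0.3; three trainees for every trainer.

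**1. The plan's own figure.** SD of change = sqrt(9.0² + 5.2² − 2r × 9.0 × 5.2).
- r = 0: sqrt(81 + 27.04) = 10.39
- r = 0.5: 7.83
- r = 0.7: sqrt(108.04 − 65.52) = 6.52
- r = −1, the maximum: 9.0 + 5.2 = 14.2

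An exact paired t-test for 16.2 points at 95% power needs 8 individuals at r = 0, 5 at r = 0.7 and at most 13 at r = −1. The stated 23 is not reproduced. It matches a standardized change of 0.8, that is, an SD of change near 16.2 / 0.8 = 20, above the maximum of 14.2. That is a separate matter. Here it means only that 23 is more than the stated inputs require, so power for 16.2 points exceeds 99.9% at any r.

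**2. Smallest observed mean gain that is significant.** Threshold = t × SD / sqrt(n). With clustering, threshold = t(0.975, 23) × SD × sqrt((1 + 2 × ICC) / 72), using 24 trainers − 1 = 23 df.

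| Setting | Calculation | Threshold | Share of 16.2 |
|---|---|---|---|
| 72 independent, r = 0 | 1.994 × 10.39 / sqrt(72) | 2.44 | 15% |
| 72 independent, r = 0.7 | 1.994 × 6.52 / sqrt(72) | 1.53 | 9% |
| 72, ICC 0.1, r = 0 | 2.069 × 10.39 × sqrt(1.2 / 72) | 2.78 | 17% |
| 72, ICC 0.3, r = 0 | 2.069 × 10.39 × sqrt(1.6 / 72) | 3.21 | 20% |
| 23 independent, r = 0 | 2.074 × 10.39 / sqrt(23) | 4.49 | 28% |
| 23 independent, r = 0.7 | 2.074 × 6.52 / sqrt(23) | 2.82 | 17% |

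Each threshold is also the half-width of the 95% CI. At r = 0, allowing for clustering widens it from 2.44 to 2.78 or 3.21, a factor of 1.14 or 1.32.

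**3. Chance that a given true gain is significant.** With 72 independent trainees:
- 1 point: 13% to 19% (r = 0 to 0.5)
- 2 points: 36% to 57% (r = 0 to 0.5)
- 3 points: 68% to 97% (r = 0 to 0.7)
- 5 points: at least 98% (r = 0 to 0.7)

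With 23 trainees, a true 3-point gain is significant 26% to 56% of the time (r = 0 to 0.7).

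**4. The 75% rule.** With 72 participants, 0.75 × 72 = 54 must succeed. Binomial tail for one task: 5% chance of passing if true success is 65%, 22% at 70%, 56% at 75%, 88% at 80%. The rule refers to participants without saying which group. With the 24 trainers (18 needed), the chance at 70% is 39%. The observed percentage alone therefore does not establish 75%, and anyone who could already do the task counts as a success.

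**The case against.** Six points can be made for the plan.

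- **There is a benchmark.** The 75% rule is fixed in advance, is not self-report, and is the only explicit success criterion in 2.18. A reader who looks only at the paired tests might infer that the plan has no bar above zero; the text contradicts that. The rule still does not address attribution, because it has no comparator, baseline or confidence bound. The recordings are also self-selected: 5.8.2 and 5.15 let participants decline, re-record or withhold videos.
- **The paired test is not a formality.** A reader might infer that almost any gain would pass. Step 3 shows otherwise: true gains of 1 or 2 points often fail even with 72 trainees.
- **The 16.2 points are not a pass mark.** They are a WSTP score difference in Occupational Therapy students, while the trial measures trainees' WST-Q totals. The documents do not show that population, scale or amount of training match. This stands. It also means the shares in step 2 show scale only, since they borrow those SDs.
- **The plan claims less than it might.** Aim 1.2 is already framed as the ability of remotely trained clinicians to teach others. No section claims equivalence to other formats, and none says that a significant paired test alone proves effectiveness. This stands, but 1.1 and 2.17 still use that word and nothing limits it.
- **Trainer data are only partly available.** A reader of 6.2.2 might infer that a full trainer pre-post dataset is in hand. Trainers who did the earlier activities in a previous study are paid here only for the modules and a pre/post confidence questionnaire. With at most 24 trainers, relating trainer change to trainee change would be weak evidence, and it is not recommended.
- **A comparator might appear elsewhere.** This is a coordinating-center application that excludes local site activities. The item covering randomization (CC2.3) is answered yes, but its description covers only templates and enrollment tracking. Nothing in the objective, analysis or sizing text implies a second arm.

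**Conclusion.** The point holds as a mismatch between the stated purpose and what the analysis can support. As written, 2.18 can show whether trainees of remotely trained trainers score higher than at baseline. It cannot credit that gain to the remote training.

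An observed mean gain of 1.5 to 4.5 points, depending on n, correlation and ICC, would be significant: 9% to 28% of the planning gain, or roughly a tenth to a quarter. This rests on two-sided 0.05, on the students' SDs carrying over to trainees' WST-Q, and on the assumed correlations and ICCs, none of which the documents give.

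A reader might go further and infer that remote training does not work, or that the study is worthless without a control arm. The documents support neither. An uncontrolled study can answer the narrower question well if it is stated as such and the interval respects clustering.

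**What to change.** 1. In 1.1 and 2.18 (and to match, 2.17), limit the conclusion to whether trainees of remotely trained trainers improve. State that the gain will not be credited to the remote format and that no equivalence to other formats is claimed.
2. In 2.18, make the main result the mean trainee change with a 95% CI that accounts for clustering by trainer (a mixed model with a trainer effect, or cluster-robust standard errors), reported alongside the 75% per-task result.
3. Cite the 16.2-point gain only as planning context, noting the different population and possibly different scale.
4. Optionally, summarise trainers' own pre/post questionnaires descriptively where this study collects them.

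The cost is wording and a little more analysis, with no new participants or visits. The downside is a more modest claim and a wider interval, by about 14% to 32% under the assumed ICCs of 0.1 to 0.3.
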